6.4.2. Secondary Efficacy Analyses

(i) Transplant-Related Mortality (TRM) for Non-Malignant patients or Non-Relapse Mortality (NRM) for Malignant patients at 100 and 180 days

This analysis is intended to characterize the contribution of Time-to-Transplant-Related Mortality (TRM) or Non-Relapse Mortality (NRM) to the composite EFS endpoint. TRM/NRM will be estimated using a Nelson-Aalen cumulative incidence function at days 100 and 180. An event for this endpoint is death without evidence of disease recurrence. Recurrence of disease or relapse will be considered a competing event. Cumulative incidence plots with descriptive summary statistics including incidence and 95% confidence intervals will be presented. If there is sufficient data, the analysis may be repeated by type of disease (malignant or non-malignant).

(ii) Cumulative Incidence and Severity of grade 2-4 acute organ GvHD and moderate - severe chronic GvHD at 180 days

This analysis is intended to characterize the contribution of acute or chronic GvHD to the composite EFS endpoint. Severity of acute and chronic GvHD will be summarized and further in the analysis of safety data. Cumulative incidence of GvHD at day 180 will be estimated from time of transplant using a Nelson-Aalen cumulative incidence function and treating death prior to GvHD as a competing risk.

Cumulative incidence plots with descriptive summary statistics including incidence and 95% confidence intervals will be presented. If there is sufficient data, the analysis will be repeated for each type of disorder (malignant or non-malignant) stratification.

Depending on the number of events, additional GvHD severity subgroups to be analysed include acute grade 1-4 GvHD, grade 2-4 GvHD including skin-only presentation, grade 3-4 GvHD, mild-severe chronic GvHD, and, severe chronic GvHD. The same statistical methods and summary statistics described above will be applied to these analyses.

(iii) Time to Resolution of Acute or Chronic GvHD After Administration of Rimiducid (including Response to Rimiducid)

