The resolution of acute GvHD (aGvHD) or chronic GvHD (cGvHD) after administration of rimiducid will be based on the response grading of the GvHD criteria provided in the protocol. The event for this endpoint is any patient who achieved a best overall response (BOR, i.e., either a Complete Response (CR) or Partial Response (PR)) based on aGvHD grading. Only patients experiencing aGVHD who received rimiducid (AP1903) infusion for treatment will be considered for this endpoint. Best overall resolution of aGVHD is defined from the date of AP1903 infusion. The percentage of patients with acute or chronic GvHD, the number of doses of rimiducid, and the best overall response to rimiducid within 7 and 30 days will be presented in listings and summarized. Concomitant medication usage in subjects with acute or chronic GvHD and, further, among those subjects who went on to receive rimiducid, will also be summarized.

Additional analysis and summary statistics will be conducted for resolution of chronic GvHD after administration of rimiducid as well as any case of GvHD (acute or chronic).

(iv) Immune reconstitution as determined by T cell subset counts at day 180

- a. Median and range of CD3 counts at 30, 60, 100 and 180 days
- b. Median and range of CD4 counts at 30, 60, 100 and 180 days
- c. Median and range of CD8 counts at 30, 60, 100 and 180 days

Quantitative assessment of each immune T-cell counts will be performed at various visit time points after transplant as captured in clinical database up to day 180 of follow-up. Analysis and statistical summaries will be performed separately for each T cell subtype assessed. The pattern of each immune reconstitution lab counts will be summarized using graphical summaries and descriptive statistic summary tables including mean (standard deviation), median, and range (minimum, maximum) across the time points assessed. Plots of mean and median cell counts representing measurements over time will be generated to visualize general patterns over time of immune reconstitution.

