7.1.1. Planned Data Outputs

The following outputs are intended to be produced for the study (NB: Numbering is indicative only and may be updated based on CSR requirements):

Tables:

- 14.1.1.1 Number of Subjects by Analysis Population and Disposition
- 14.1.1.2 Summary of Study Analysis Populations
- 14.1.1.3 Major Protocol Deviations and Violations
- 14.1.2.1 Subject Demographics at Baseline
- 14.1.2.2 Baseline Primary Disease Type, Conditioning and Treatment History
- 14.1.2.3 Donor Demographics, Relationships and HLA Typing
- 14.1.4.1 Prior Medications Use
- 14.1.4.2 Concomitant Medications Use
- 14.1.5 Study Treatment Exposure
- 14.2.1.1 Kaplan-Meier Parameter Estimates of Event-Free Survival
- 14.2.1.2 Kaplan-Meier Parameter Estimates of Event-Free Survival: Sensitivity Analysis for Any Grade 2-4 Acute GvHD
- 14.2.1.3 Kaplan-Meier Parameter Estimates of Event-Free Survival: Sensitivity Analysis on Dosing Window
- 14.2.1.4 Kaplan-Meier Parameter Estimates of Event-Free Survival: Sensitivity Analysis for Death from Any Cause
- 14.2.1.5 Kaplan-Meier Parameter Estimates of Event-Free Survival: Sensitivity Analysis for Dose in Subjects with Malignant Disease
- 14.2.2 Cumulative Incidence Function Parameters Time to Transplant-Related or Non-Relapse Mortality
- 14.2.3.1 Cumulative Incidence Function Parameters Time to Acute GvHD Grades 2-4

- 14.2.3.1.1 Cumulative Incidence Function Parameters Time to Acute GvHD: Grade 2 Organ, Grades 3-4
- 14.2.3.2 Cumulative Incidence Function Parameters Time to Acute GvHD Grades 3-4
- 14.2.3.3 Cumulative Incidence Function Parameters Time to Severe Chronic GvHD
- 14.2.3.3.1 Cumulative Incidence Function Parameters Time to Moderate or Severe Chronic GvHD
- 14.2.3.4 Cumulative Incidence Function Parameters Time to Chronic GvHD Mild-Severe

- 14.2.4.1 Kaplan-Meier Parameter Estimates of Time to Resolution of Acute GvHD After Rimiducid Administration
- 14.2.4.2 Kaplan-Meier Parameter Estimates of Time to Resolution of Chronic GvHD After Rimiducid Administration
- 14.2.4.3 Kaplan-Meier Parameter Estimates of Time to Resolution of GvHD (Acute or Chronic) After Rimiducid Administration
- 14.2.4.4 Best Overall Clinical Response to Rimiducid in Subjects with Acute or Chronic GvHD
- 14.2.4.5 GvHD Types and Grades
- 14.2.5 Immune Reconstitution
- 14.2.6 Cumulative Incidence Function Parameters of Time to Immune Reconstitution of CD3, CD4, and CD8 T-cell Counts

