- 14.2.1.5 Kaplan-Meier Parameter Estimates of Event-Free Survival: Sensitivity Analysis for Dose in Subjects with Malignant Disease
- 14.2.2 Cumulative Incidence Function Plot of Time to Transplant-Related or Non-Relapse Mortality
- 14.2.3.1.1 Cumulative Incidence Function Parameters Time to Acute GvHD: Grade 2 Organ, Grades 3-4
- 14.2.3.1 Cumulative Incidence Function Plot of Time to Acute GvHD Grades 2-4
- 14.2.3.2 Cumulative Incidence Function Plot of Time to Acute GvHD Grades 3-4
- 14.2.3.3.1 Cumulative Incidence Function Parameters Time to Moderate or Severe Chronic GvHD
- 14.2.3.3.2 Cumulative Incidence Function Plot of Time to Severe Chronic GvHD
- 14.2.3.3.3 Cumulative Incidence Function Plot of Time to Overall (Mild-to-Severe) Chronic GvHD
- 14.2.4.1 Kaplan-Meier Plot of Time to Resolution of Acute GvHD After Rimiducid Administration

- 14.2.4.2 Kaplan-Meier Plot of Time to Resolution of Chronic GvHD After Rimiducid Administration
- 14.2.4.3 Kaplan-Meier Plot of Time to Resolution of GvHD (Acute or Chronic) After Rimiducid Administration
- 14.2.5.1 Plot of of CD3 T Cell Counts Across Study Visit Time Points to 180 Days
- 14.2.5.2 Plot of of CD4 T Cell Counts Across Study Visit Time Points to 180 Days
- 14.2.5.3 Plot of of CD8 T Cell Counts Across Study Visit Time Points to 180 Days
- 14.2.5.4.1 Plot of CD3+CD19+ T Cell Counts Across Study Visit Time Points to 180 Days
- 14.2.5.4.2 Plot of the Proportion of CD3+CD19+ T Cells Across Study Visit Time Points to 180 Days
- 14.2.5.4.3 Plot of CD3+CD19+ T Cell Counts Before and After Treatment with Rimiducid
- 14.2.5.4.4 Plot of the Proportion of CD3+CD19+ T Cells Before and After Treatment with Rimiducid
- 14.2.5.5 Plot of B Cell Counts Across Study Visit Time Points to 180 Days
- 14.2.5.6 Plot of NK Cell Counts Across Study Visit Time Points to 180 Days
- 14.2.5.7 Plot of Immunoglobulin A Levels Across Study Visit Time Points to 180 Days
- 14.2.5.8 Plot of Immunoglobulin M Levels Across Study Visit Time Points to 180 Days
- 14.2.5.9 Plot of Immunoglobulin G Levels Across Study Visit Time Points to 180 Days
- 14.2.6.1 Cumulative Incidence Function Plot of Time to Immune Reconstitution of CD3 T-cell Count
- 14.2.6.2 Cumulative Incidence Plot of Time to Immune Reconstitution of CD4 T-cell Count
- 14.2.6.3 Cumulative Incidence Plot of Time to Immune Reconstitution of CD8 T-cell Count
- 14.2.7 Kaplan-Meier Plot of Time to Disease-Free/Chronic-GvHD-Free Survival

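### Time to GvHD resolution after rimiducid is planned as Kaplan-Meier with no rule for death; run as written, deaths without response are censored and the response probability can be overstated

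*SAP*

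**What the plan says.** SAP 6.4.2(iii) defines the endpoint: "The event for this endpoint is any patient who achieved a best overall response", meaning a complete or partial response. On the time origin it says "Best overall resolution of aGVHD is defined from the date of AP1903 infusion". It adds that chronic GvHD, and any GvHD, will be analysed as well. It names no estimator, no censoring rule and no handling of death.

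The estimator appears only in SAP 7.1.1:
- Table 14.2.4.1: "Kaplan-Meier Parameter Estimates of Time to Resolution of Acute GvHD After Rimiducid Administration"
- Table 14.2.4.2: "Kaplan-Meier Parameter Estimates of Time to Resolution of Chronic GvHD After Rimiducid Administration"
- Table 14.2.4.3: "Kaplan-Meier Parameter Estimates of Time to Resolution of GvHD (Acute or Chronic) After Rimiducid Administration"
- Figures 14.2.4.1 to 14.2.4.3 follow suit, the first being "Kaplan-Meier Plot of Time to Resolution of Acute GvHD After Rimiducid Administration"

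Two general rules bear on this. SAP 6.2.1 allows Kaplan-Meier or Nelson-Aalen methods as suits the endpoint. SAP 6.2.2 censors withdrawn patients at their last documented visit. Neither says what happens to a patient who dies before responding. Protocol 10.4.5.3 mentions time to resolution of chronic GvHD after rimiducid and names no estimator.

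**The concern.** Kaplan-Meier treats a censored patient as someone who could still have the event. A patient who dies with active GvHD cannot. If that death is censored, the patient's weight passes to those still at risk. The curve then estimates response in a hypothetical setting without death, not the share of treated patients who responded. The error runs one way, in the product's favour, and a median read from the same curve can only be equal or too early.

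The SAP sets a different standard for comparable endpoints. For GvHD onset it specifies "treating death prior to GvHD as a competing risk". It also makes death a competing event for immune reconstitution and for neutrophil and platelet engraftment (6.4.2(v), 6.4.3(ii)-(iii)) and for leukemia relapse (6.4.3(i)). For disease-status recovery the competing event is non-recurrence mortality (6.4.2(vii)).

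Evaluating rimiducid for GvHD is the SAP's secondary objective (3.1), and these are the only time-to-event outputs listed for it.

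**Working it through.** The plan states no rate, sample size or power for this endpoint, so there is no figure to reproduce. The documents give neither the number treated with rimiducid nor mortality before response. All rates and data below are therefore assumptions.

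**1. Constant hazards.** Let r be the value of 1-KM at the horizon with deaths censored, and q the net probability of death over the same period.
- a = -ln(1-r) and b = -ln(1-q)
- Cumulative incidence (CIF) = a/(a+b) × [1 - exp(-(a+b))], where exp(-(a+b)) = (1-r)(1-q)

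Example with r = 0.70 and q = 0.10: a = 1.204 and b = 0.105, so a/(a+b) = 0.920. The bracket is 1 - 0.30 × 0.90 = 0.730. CIF = 0.671, so 1-KM is 2.9 points too high.

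CIF, with the overstatement in points in brackets:

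| 1-KM | q = 5% | q = 10% | q = 20% | q = 30% |
|---|---|---|---|---|
| 0.50 | 0.489 (1.1) | 0.477 (2.3) | 0.454 (4.6) | 0.429 (7.1) |
| 0.70 | 0.686 (1.4) | 0.671 (2.9) | 0.641 (5.9) | 0.609 (9.1) |
| 0.80 | 0.785 (1.5) | 0.770 (3.0) | 0.738 (6.2) | 0.704 (9.6) |
| 0.90 | 0.885 (1.5) | 0.870 (3.0) | 0.839 (6.1) | 0.805 (9.5) |

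With q = 0 the two agree.

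**2. A small treated group.** Take 20 treated patients, of whom 14 respond, on days 1, 2, 3, 5, 7, 7, 10, 14, 14, 21, 21, 28, 40 and 60. The observed share is 14/20 = 0.700. Patients who neither respond nor die are followed to day 180.

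| Deaths without response | 1-KM | Aalen-Johansen CIF |
|---|---|---|
| None | 0.700 | 0.700 |
| 2 (days 12, 25) | 0.752 | 0.700 |
| 4 (days 6, 12, 25, 35) | 0.830 | 0.700 |
| 6 (days 6, 9, 12, 25, 35, 50) | 1.000 | 0.700 |
| 4, all after the last response (days 70, 90, 100, 150) | 0.700 | 0.700 |

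For the row with deaths on days 6, 12, 25 and 35, the Kaplan-Meier product is (16/20)(12/15)(7/11)(5/6)(2/4) = 0.170, so 1-KM = 0.830. Keeping deaths at risk to day 180 without an event also returns 0.700 in every row. The gap therefore comes from censoring deaths that occur before someone else's response.

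**3. Dependence on horizon.** Assume response at 1% or 2% per day and death without response at 0.5% per day. Then CIF(t) = r/(r+d) × [1 - exp(-(r+d)t)] and 1-KM = 1 - exp(-rt), where r and d are now the daily rates.
- Day 7: 6.6% against 6.8%, or 12.8% against 13.1%
- Day 30: 24.2% against 25.9%, or 42.2% against 45.1%
- Day 180: 62.2% against 83.5%, or 79.1% against 97.3%

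**The case against.** **The SAP never says that deaths are censored here.** That is correct, and a reader should not take it as stated. It follows from naming Kaplan-Meier for an event that excludes death while giving no other rule. The bias would vanish if deaths were kept at risk to the horizon, but no such rule is written. The freedom of choice in 6.2.1 does not help, because the six output titles have already made the choice.

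**A reader might infer an error of about 20 points.** The Day 180 figures above differ by 21.3 and 18.2 points, but a death rate of 0.5% per day means net mortality of 1 - exp(-0.9) = 59%. No document supports that rate, and 6.4.2(iii) sets no Day 180 read-out after rimiducid. Its windows are 7 and 30 days, where the same rates give gaps of at most 2.9 points. The earlier Phase I trial (Protocol 4.1.3) reports resolution of acute GvHD within a day in very few patients. If responses are that fast, little room is left for competing deaths.

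**A reader might infer that this is the SAP's sole departure.** It is not. The time-to-infection outputs (14.2.12.1 and 14.2.12.2) name neither an estimator nor a competing event. The contrast holds for the endpoints listed under the concern.

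**A reader might infer that the treated patients are the sickest.** Rimiducid eligibility includes uncontrolled Grade I or II skin-only acute GvHD (SAP 4.1) and mild chronic GvHD (Protocol Appendix B). High mortality cannot be presumed.

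**Other planned outputs mitigate.** The 7- and 30-day best-response summaries and Table 14.2.4.4 avoid the bias if all treated patients stay in the denominator. This stands, but those summaries do not correct the curves and could visibly disagree with them.

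**Conclusion.** The point holds as a method named wrongly for this event, and it should be corrected. If deaths without response are censored, 1-KM is never below the cumulative incidence, and exceeds it whenever such a death precedes another patient's response.

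The size is unknown from the documents and may be zero. Under constant hazards with 1-KM between 50% and 90%, it is 1.1 to 1.5 points at 5% net mortality and 7.1 to 9.6 points at 30%. It is small if responses come within days. In a small group a few early deaths can make it large: 13 points in the assumed set of 20 with four early deaths.

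The consequence is limited. The endpoint is secondary and descriptive, and neither the primary EFS analysis nor the non-inferiority power calculation depends on it.

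**What to change.** In SAP 6.4.2(iii), specify the Aalen-Johansen cumulative incidence of complete or partial response from the first rimiducid dose. Make death before response the competing event, and censor living non-responders at their last assessment. Naming the first dose also settles the time origin, since SAP 4.1 allows up to three doses.

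Change Tables and Figures 14.2.4.1 to 14.2.4.3 to match. Retitling alone is not enough: SAP 7.1 treats title changes as minor but requires a true change of method to be documented. For the 7- and 30-day summaries and Table 14.2.4.4, state that all treated patients remain in the denominator.

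The cost is SAP wording and an analysis option. No new data are needed, because deaths are already summarised and listed (Table 14.3.2.8, Listing 16.2.7.5). The downside is that reported resolution probabilities may be lower.

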3.2. Study Endpoint(s)

Endpoints will be further defined in subsequent sections. Unless otherwise specified, time-to-event endpoints will be calculated from the date of HSC infusion. If a patient received more than one HSCT, the time of the last HSC infusion immediately preceding infusion with BPX-501 will be the transplant date.

Primary Endpoint:

Event-Free Survival (EFS) at 180 days. Events are defined as the first occurrence of either transplant-related mortality (TRM) for non-malignant patients or non-relapse mortality (NRM) for malignant patients, severe GvHD (Grade 2-4 acute organ GvHD or extensive/moderate-severe chronic GVHD), and life-threatening infections (Grade 4).

NB: In the BPX-501 protocols, the terminology 'extensive' chronic GvHD was used. For the purposes of the primary analysis and for the rest of this SAP, extensive chronic GvHD will be defined as moderate or severe chronic GvHD. 'Overall' chronic GvHD or chronic GvHD without a qualifier will be interpreted as mild, moderate or severe chronic GvHD.

The following secondary endpoints are in the BP-004 protocols, although additional endpoints and analyses are described below in subsequent sections of this document.

Secondary Endpoints:

- (i) Transplant-Related Mortality (TRM) in patients with non-malignant diagnoses or Non-Relapse Mortality (NRM) in patients with malignant diagnoses at 100 and 180 days
- (ii) Cumulative incidence and severity of acute GvHD (any Grade 2-4 or Grade 3-4) as well as overall and moderate-severe chronic GvHD at 180 days.
- (iii) Time to resolution of acute GvHD after administration of rimiducid
- (iv) Immune reconstitution as determined by T cell subsets up through 180 days
 - a. Absolute CD3 count
 - b. Absolute CD4 count

- c. Absolute CD8 count
- (v) Time-to-immune reconstitution defined by CD3 count > 500 cells/uL; CD4 count > 200 cells/uL; CD8 count of 200 cells/uL
- (vi) Disease-Free/chronic GvHD Survival (DFGS) defined as the first of either disease recurrence, death from any cause, or chronic GVHD
- (vii) Disease status within the following disease indications at 180 days:
 - a. Primary immune disorders as determined by CD3 T cell count ≥ 500 cells/uL and normal levels of IgA and IgM
 - b. Haemoglobinopathies as determined by incidence of RBC transfusion independence for 8 consecutive weeks and untransfused haemoglobin of ≥ 8.5 g/dL

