4.1. Definition of Study Drugs

The study drugs are:

- BPX-501: *Donor T cells genetically modified with BPZ-1001 retroviral vector containing the iC9 suicide gene, and*
- Rimiducid (AP1903): *Dimerizer drug used in case of a patient developing GvHD*

The BPX-501 T cell infusion is administered 14 days (+/-4 days) after completion of the stem cell allograft infusion. Under certain protocol versions, subjects may have been administered BPX-501 within 21 days (+/- 14 days) after completion of the stem cell allograft infusion. Subjects with uncontrolled Grade I or II skin-only, Grade II (non-skin), III, or IV acute GvHD were eligible to receive up to three doses of rimiducid at 0.4 mg/kg as a 2-hour intravenous (I.V.) infusion. Chronic GvHD, under conditions specified by protocol, will be treated with an infusion of rimiducid in individuals who have not previously received an infusion of rimiducid.

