6. STATISTICAL METHODS AND DATA HANDLING

6.1. Analysis Populations

The following analysis populations are defined for the study:

(i) *Enrolled Population (EP)* – Defined as all patients who signed informed consent, were assessed for inclusion/exclusion criteria during the screening period, and who were considered eligible for enrollment and post-enrollment follow-up. This population will be used to present overall study disposition data and for summarizing the total number of patients screened and considered eligible for the study.

(ii) *HSCT Safety Population (HSP)* – Defined as all patients in the enrolled population (EP) who received Hematopoietic Stem Cell Transplantation (HSCT). Only SAEs were reported in subjects prior to receiving BPX-501. The HSP therefore represents the analysis population for certain analyses of SAEs as well as disposition and outcomes in subjects who did not go on to receive BPX-501 for any reason.

(iii) *BPX-501 Safety Population (BSP)* – Defined as all patients who received HSCT and went on to receive any dose of BPX-501. Unless otherwise specified, this will be the default primary safety analysis population.

(iv) *Intent-to-treat Population (ITT)* – Given that this is a single-arm study, a “Full Analysis Set” (FAS) population is proposed to serve as the ITT population from which to provide estimates of treatment effects in subjects receiving BPX-501. The FAS/ITT population includes all patients treated with HSCT who received BPX-501 at the dose of 1×10^6 cells/kg.

(v) *Per Protocol Populations (PP)* – Defined as all patients in the ITT/FAS analysis population who were infused with BPX-501 at the dose of at least 1×10^6 cells/kg within a dosing around Day 14 (+/- 4 days) or Day 21 (+/- 14 days) after HSCT. The primary and key secondary efficacy analyses may be repeated on the PP populations as a means of characterizing the robustness of any outcome results.

(vi) *Rimiducid Population (RP)* – Defined as all patients who received at least one dose of rimiducid for the treatment of acute or chronic GvHD.

(vii) *Rimiducid Pharmacokinetics Population (RPK)* – Defined as all patients who received at least one dose of rimiducid for the treatment of acute or chronic GvHD and have a plasma sample to measure rimiducid concentrations over time.

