6.3.4. Treatment Exposure

Study treatment data including dose level of BPX-501 and rimiducid dosing (AP1903) information will be presented by type of disorder (malignant or non-malignant) and presented as patient data listings for the appropriate safety and ITT (FAS) populations.

Days on study will be calculated using the HSCT date as the reference date. The days on study for the date of interest will be calculated as (date of interest – date of HSCT + 1) for dates later than HSCT. For dates earlier than HSCT, the days on study will be calculated as (date of interest – date of HSCT).

Data listings will present study days in addition to assessment dates. Study day 1 is defined in section 6.2.3. For efficacy and safety endpoints the same rule for study day will apply.

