6.5. Safety Endpoints

Data for adverse events (AEs), serious adverse events (SAEs), clinical laboratory parameters, vital signs, and physical examinations will be presented in subject listings, including assessments of abnormality and clinical significance, where applicable. Summaries will be prepared for key variables (detailed below) by study visit (where applicable) for all patients as well as by malignant/non-malignant disease status. No inferential statistical testing will be performed for safety variables.

Unless otherwise specified, safety analyses will be conducted primarily within the BPX-501 safety population. Additional safety listings will be provided focusing (i) on the subjects enrolled into the initial dose escalation portion of the study, and on the subjects enrolled into the study but who either (ii) did not receive HSCT, or who (iii) received HSCT but did not receive BPX-501. Only SAEs were collected prior to administration of BPX-501.

For the purposes of analysis, treatment-emergent adverse events will be defined as those AEs with onset or worsening date occurring on or after the date of infusion with BPX-501.

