- 14.2.7 Kaplan-Meier Parameter Estimates of Time to Disease-Free/Chronic-GvHD-Free Survival

- 14.2.8.1-3 Cumulative Incidence Function Parameters of Time to Recovery of Primary Immune Disorders as Determined by CD3 T Cell Count >500 cells/uL, and Normal Levels of IgA and IgM

- 14.2.8.2 Cumulative Incidence Function Parameter Estimates of Time to Recovery of Haemoglobinopathies as Determined by Incidence of RBC Transfusion Independence and Haemoglobin of >8.5 g/dL
- 14.2.8.3-3 Cumulative Incidence Function Parameter Estimates of Time to Recovery of Fanconi Anemia as Determined by RBC > 3,000,000 cells/uL, Neutrophil Count > 1500 cells/uL, and Platelet Count >150,000
- 14.2.8.4 Kaplan-Meier Parameter Estimates of Relapse-Free Survival in Subjects with Leukemia
- 14.2.8.5 Cumulative Incidence of Relapse in Subjects with Acute Leukemia
- 14.2.9 Cumulative Incidence Function Parameter Estimates of Time to Neutrophil Engraftment
- 14.2.10 Cumulative Incidence Function Parameter Estimates of Time to Platelet Engraftment
- 14.2.11 Graft Failures

- 14.2.12.1 Time to Any Grade Infection
- 14.2.12.2 Time to Grade 3 or Higher Infection
- 14.2.13.1 Kaplan-Meier Parameter Estimates of Overall Survival
- 14.2.13.2 Kaplan-Meier Parameter Estimates of Disease-Free Survival in Subjects with Non-Malignant Disease
- 14.2.13.3 Sensitivity Analysis: Kaplan-Meier Parameter Estimates of Disease-Free Survival, by Dosing Window
- 14.2.13.4 Kaplan-Meier Parameter Estimates of Relapse-Free Survival in Subjects with Malignant Disease
- 14.2.13.5 Sensitivity Analysis: Kaplan-Meier Parameter Estimates of Relapse-Free Survival, by Dosing Window in Subjects Dosed at 1×10^6 Cells/kg
- 14.2.13.6 Sensitivity Analysis: Kaplan-Meier Parameter Estimates of Relapse-Free Survival, by Dosing Window in Subjects Dosed at 1×10^6 Cells/kg or Above
- 14.3.1.1 Treatment-Emergent Adverse Events Summary
- 14.3.1.2 Treatment-Emergent Adverse Events Regardless of Relationship to Study Treatment by System Organ Class, Preferred Term, and Dose of BPX-501
- 14.3.1.3 Treatment-Emergent Adverse Events Related to Occurring After AP1903 Administration, by System Organ Class, Preferred Term, and Dose of BPX-501
- 14.3.1.4.1 Treatment-Emergent Adverse Events Regardless of Relationship to Study Treatment, by System Organ Class, Preferred Term, and Maximum Severity
- 14.3.1.4.2 Treatment-Emergent Adverse Events Occurring After AP1903 Administration, by System Organ Class, Preferred Term, and Maximum Severity

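### Infection outputs 14.2.12.1-2 start at HSC infusion by default, but only SAEs were captured before BPX-501, so if they use AE records, early non-serious infections cannot appear

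*SAP*

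**What the plan says.** **Outputs.** SAP 7.1.1 plans a table and a figure for each of "14.2.12.1 Time to Any Grade Infection" and "14.2.12.2 Time to Grade 3 or Higher Infection". The titles give no time origin, population, estimator or data source. SAP 6.4.3(v), the text on infectious complications, defines the events and promises tables and listings, but is silent on the same four items.

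**Time origin.** SAP 3.2 sets the default: "Unless otherwise specified, time-to-event endpoints will be calculated from the date of HSC infusion". SAP 6.3.4 uses HSCT as the reference date and adds: "For efficacy and safety endpoints the same rule for study day will apply". Nothing overrides this for the two infection outputs.

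**Event capture.** SAP 6.5 states: "Only SAEs were collected prior to administration of BPX-501". SAP 6.1, under the HSCT Safety Population, says the same: "Only SAEs were reported in subjects prior to receiving BPX-501".

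**Timing of BPX-501.** SAP 4.1 gives the standard schedule: "The BPX-501 T cell infusion is administered 14 days (+/-4 days) after completion of the stem cell allograft infusion". It adds that, under certain protocol versions, "subjects may have been administered BPX-501 within 21 days (+/- 14 days) after completion of the stem cell allograft infusion".

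**The concern.** The clock starts at transplant, while all-grade event capture starts only at BPX-501 infusion. Between the two dates a patient with a non-serious infection is counted as at risk and infection-free. That patient's first infection is then dated to a later episode, or the patient is never counted. The rule for what counts as an observed event therefore changes partway along the curve, on a date that differs between patients.

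The direction of the error is fixed: early incidence too low, time to first infection too long. It matters for interpretation because SAP Section 2 names infection as a limitation of T-cell-depleted haploidentical transplant and gives immune reconstitution as a purpose of BPX-501. An artificially quiet opening to the any-grade curve could be read as a treatment benefit.

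**Working it through.** The plan states no figure for these outputs, so there is none to reproduce. The check has three parts.

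**1. Length of the gap** (from SAP 4.1)

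- Standard window: 14 - 4 = Day 10 to 14 + 4 = Day 18, or 1.4 to 2.6 weeks. As a share of 180 days: 10/180 = 5.6% to 18/180 = 10.0%.
- Wider window: 21 - 14 = Day 7 to 21 + 14 = Day 35, or 1 to 5 weeks. As a share of 180 days: 7/180 = 3.9% to 35/180 = 19.4%.

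**2. Non-serious infections concentrated early**

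All rates here are assumptions; the documents give none. Infusion is fixed at Day 14. Let p be the proportion with a non-serious infection by Day 14, and let 60% have one over the next 166 days, independently of what happened before. Only non-serious infections are modelled.

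- Hazard after infusion: λ = -ln(1 - 0.60)/166 = 0.916/166 = 0.00552 per day.
- True incidence at Day t: 1 - (1 - p) × exp(-λ(t - 14)).
- Reported incidence at Day t: 1 - exp(-λ(t - 14)), because nothing non-serious before Day 14 is captured.
- At Day 30, exp(-0.00552 × 16) = 0.915. At Day 180 the factor is 0.40.

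| p | Day 30 true | Day 30 reported | Day 180 true | Day 180 reported |
|---|---|---|---|---|
| 10% | 1 - 0.9 × 0.915 = 17.6% | 8.5% | 1 - 0.9 × 0.4 = 64% | 60% |
| 30% | 1 - 0.7 × 0.915 = 35.9% | 8.5% | 1 - 0.7 × 0.4 = 72% | 60% |
| 50% | 1 - 0.5 × 0.915 = 54.2% | 8.5% | 1 - 0.5 × 0.4 = 80% | 60% |

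The shortfall is p times the factor, so at Day 180 it is 0.4p: 4, 12 or 20 percentage points.

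**3. No early excess**

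Now assume a constant hazard over 180 days and a true 180-day incidence C of first non-serious infection of 30%, 50% or 70%. Then λ = -ln(1 - C)/180, and the share of first events falling before infusion day d is (1 - exp(-λd))/C.

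- d = 14: 9%, 11% and 13%.
- d = 35: 22%, 25% and 30%.

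A higher hazard soon after transplant would raise these shares.

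**Grade 3+ output and EFS.** A life-threatening event is serious, as is one that requires or prolongs hospitalisation (protocol 9.1.3, the follow-up study's definition). Grade 4 infections, and those Grade 3 infections that meet a seriousness criterion, would therefore be captured before BPX-501. What is lost is mainly non-serious Grade 3. The infection component of primary EFS is Grade 4 only (SAP 6.4.1). No size can be given for the Grade 3+ output, because the documents do not give the serious share of Grade 3 infections.

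**The case against.** The strongest objection is that the AE database as source is an inference. The two outputs sit among the efficacy tables and pair with 6.4.3(v), which defines events by clinical criteria such as viral reactivation and need for treatment. SAP 7.1.1 plans an efficacy listing of infectious complications with severity and timing (16.2.6.9), separate from the infection AE listing (16.2.7.6). SAP 4.4 refers to scheduled microbiological investigations, and SAP 6.3.7 lists prior and concomitant medications with indication and dates in the HSCT Safety Population. The SAP was written for BP-004, and that protocol is not among the documents, so its collection forms cannot be checked.

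This stands as a reason to state the bias conditionally. It does not remove the point. No section says that non-serious infections were recorded in full from Day 0, a medication record carries no infection grade, and the general statement in 4.4 that AEs are followed throughout does not displace the two specific SAE-only statements. If a fuller source exists, the SAP needs to name it.

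Four stronger readings are tempting and are not supported:

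- **That the any-grade table would show about 8% at Day 30 where the truth is 54%.** The Day-30 figures cover non-serious infections only. Serious pre-infusion infections were collected and would appear in the table. The rates are assumed.
- **That every patient has a gap of up to five weeks.** Day 7-35 applies only under certain protocol versions; the standard window is Day 10-18.
- **That the bias favours BPX-501 in a planned comparison.** The external comparison in SAP 4.2 is on EFS. No infection comparison with an outside series is planned, so any such use is hypothetical.
- **That the primary result is compromised.** Its infection component is Grade 4, which would be reported as serious.

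**Conclusion.** The point holds in conditional form and should be acted on. Followed as written and applied to AE records, the SAP's default runs the infection clock through 10-18 days, or 7-35 days under certain protocol versions, in which non-serious infections cannot appear. The any-grade output is the one mainly affected.

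The direction is certain under that condition; the size is not. It depends on the unknown rate of early non-serious infection. The 64-80% true against 60% reported at Day 180 rests on the assumed 10-50% by Day 14 and 60% over the next 166 days, and on counting non-serious infections alone. With a flat hazard and infusion at Day 14, the share of first non-serious events lost is 9-13%. These outputs are descriptive and are not among the endpoints in SAP 3.2, which limits the consequence.

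**What to change.** In SAP 6.4.3(v), name the data source for Tables and Figures 14.2.12.1-2 and state that they are timed from BPX-501 infusion, in infused patients, with death as a competing event. This matches the treatment-emergent definition in SAP 6.5, which already governs the infection AE tables (14.3.1.5.1-2), and it suits the efficacy population, all of whom were infused.

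If a curve from HSCT is wanted, limit it to serious infections, so that one collection rule applies on both sides of the infusion date. Keep an all-infection HSCT origin only if the SAP identifies a source that recorded non-serious infections from Day 0; in that case, moving the origin would discard valid early data.

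The cost is a sentence or two of SAP text and a changed start date in the programming. The downside is that the any-grade curve no longer describes the period before BPX-501. The change does not address any limit on AE reporting after infusion, which is a separate matter.
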